#### **11.4.1.2 Compliance**

A given administration will be considered noncompliant if the patient did not take the planned dose of treatment as required by the protocol. No imputation will be made for patients with missing or incomplete data.

Treatment compliance, above-planned, and under-planned dosing percentages will be summarized descriptively (N, mean, SD, median, minimum, and maximum). The percentage of patients with compliance <80% will be summarized. In addition, the number and percentage of patients with at least 1 above-planned dosing administration will be given, as well as the number and percentage of patients with 0, >0 to 20%, and >20% under-planned dosing administrations.

#### **11.4.2 Analyses of efficacy endpoints**

Efficacy analyses will be performed on the ITT population. Statistical testing will be performed for primary endpoint and secondary endpoints at Week 26 (or Week 12 for SBP).

The superiority tests will be tested at two-sided 5% significance level.

All efficacy endpoints, other than primary and secondary efficacy endpoints, will only be summarized by descriptive statistics without formal statistical testing.

##### **11.4.2.1 Analysis of primary efficacy endpoints**

- Analysis of the primary efficacy endpoint (change from Baseline to Week 26 in HbA1c) will be performed on the ITT population, using HbA1c measurements obtained during the study, including those obtained after IMP discontinuation or introduction of rescue therapy (de facto estimand). The primary efficacy endpoint of change in HbA1c from Baseline to Week 26 will be analyzed with missing values imputed by control-based copy reference multiple imputation method under the missing not at random framework for the active treatment group. The imputation model parameters will be first derived under missing at random. Then the mean of the placebo group will be used in the imputation model for imputing values for missing data for patients in the placebo group and also the active treatment groups.
- For placebo patients, missing data will be imputed based on the placebo group data.
- For patients in the sotagliflozin groups, missing data will be imputed as if the patients were on placebo throughout the study, where all patients' measurements including the on-treatment measurements will be considered as if the measurements were from the placebo group in the imputation model.

Each of the complete datasets will be analyzed by the Analysis of Covariance (ANCOVA) model with treatment groups (sotagliflozin 400 mg, sotagliflozin 200 mg, placebo), randomization stratum of HbA1c ( $\leq 8.5\%$ ,  $> 8.5\%$ ) at Screening, randomization stratum of sex (male, female) and country as fixed effects, and Baseline HbA1c value as a covariate.

Results from each complete dataset will be combined using Rubin's formula to provide the adjusted LS mean change in HbA1c from Baseline to Week 26 for each treatment group, as well as the between-group difference (comparing sotagliflozin 400 mg vs placebo), with the corresponding standard error (SE) and the 95% confidence intervals (CI) for the difference.

Summary statistics (for Screening value, Baseline value, observed values, and observed changes from Baseline) at scheduled visits will be provided for each treatment group. The summary will include the number of observations, mean, SD, SE, minimum, median, and maximum. Graphical presentations will also be used to examine trends over time using mean values ( $\pm$ SE) and mean changes from Baseline ( $\pm$ SE) at each of the scheduled visits (using OC).

### **Assessment of treatment effect by subgroup**

Descriptive analyses will be performed on the primary endpoint to summarize the treatment effects across subgroups defined by the following Baseline or Screening factors:

- Race (White, Black or African American, Asian, American Indian or Alaska Native, Native Hawaiian or other Pacific Islander).
- Ethnicity (Hispanic, Not Hispanic).
- Age group ( $< 65$  years,  $\geq 65$  years).
- Sex (male, female).
- Baseline BMI level ( $< 30$ ,  $\geq 30$  kg/m^2).
- Baseline HbA1c ( $\leq 8.5\%$ ,  $> 8.5\%$ ).
- Baseline SBP ( $< 130$  mmHg,  $\geq 130$  mmHg).
- Country.

The treatment effects across the subgroups defined for each of these factors will be estimated for the change from Baseline to Week 26 in HbA1c in the ITT population, and using a similar approach to the analysis for the primary efficacy endpoint. The adjusted estimates of treatment mean differences (comparing sotagliflozin 400 mg versus placebo) with SE and 95% CIs will be provided as appropriate across the subgroups using contrast statements.

In the event that the subgroup factor is identical or similar to a randomization strata factor (eg, Baseline HbA1c category or sex), only the subgroup factor (as a single factor and/or an interaction term) will be included in the model to avoid the issue of collinearity in the analysis. The corresponding strata factor will not be included in the model.

#### **11.4.2.2 Analysis of secondary efficacy endpoints**

The continuous secondary efficacy endpoints (see [Section 9.1.2](#)) will be analyzed using a similar approach to the primary efficacy endpoint, with missing values imputed by control-based multiple imputation method under the missing not at random framework.

For each of the continuous secondary endpoints, each of the complete datasets will be analyzed by the ANCOVA model with treatment groups (sotagliflozin 400 mg, sotagliflozin 200 mg, placebo), randomization strata of HbA1c ( $\leq 8.5\%$ ,  $> 8.5\%$ ) at screening and sex (male, female), and country as fixed effects, and baseline secondary endpoint value as a covariate.

Results from each complete dataset will be combined to provide the adjusted LS mean change from Baseline to Week 26 (respectively, Week 12 for SBP) for each treatment group, as well as the between-group difference (comparing each sotagliflozin group vs placebo group) with the corresponding (SE) and the 95% CI.

The categorical secondary endpoint such as HbA1c responders ( $< 7.0\%$ ) at Week 26 will be analyzed using a Cochran-Mantel-Haenszel method stratified by randomization stratum of Screening HbA1c ( $\leq 8.5\%$ ,  $> 8.5\%$ ) and randomization stratum of sex (male, female).

The proportion in each treatment group will be provided, as well as the difference of proportions between each sotagliflozin group and placebo with associated 2-sided 95% CI. For HbA1c responders at Week 26, all values at Week 26 will be used to determine whether a patient is a responder or not, even if they are measured after IMP discontinuation or rescue medication use. Patients who have no HbA1c measurement at Week 26 will be treated as nonresponders.

For all secondary endpoints, summary statistics at scheduled visits will be provided for each treatment group. The summary will include the number of observations, mean, SD, SE, minimum, median, and maximum. Graphical presentations will also be used to examine trends over time using mean values ( $\pm$  SE) and mean changes from Baseline ( $\pm$  SE) at each of the scheduled visits (using OC).

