#### **9.1.4 Assessment methods of efficacy endpoints**

##### **9.1.4.1 Hemoglobin A1c**

Hemoglobin A1c will be assessed at Screening (Visit 1), Baseline (Visit 3), Week 12 (Visit 6), and Week 26 (Visit 8), Week 52 (Visit 10), Week 86 (Visit 12), and Week 104 (Visit 13) and measured by a certified Level I “National Glycohemoglobin Standardization Program” Central Laboratory.

If a patient needs to receive rescue antidiabetic medication, assessment of HbA1c should be performed before the introduction of the rescue therapy.

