## 11 STATISTICAL CONSIDERATIONS

### 11.1 DETERMINATION OF SAMPLE SIZE

The sample size/power calculations were performed based on the primary variable of change from Baseline to Week 26 in HbA1c (%).

Assuming a common standard deviation (SD) of 1.2% and using a 2-sided test at a 0.05  $\alpha$ -level, 360 patients (120 patients per arm) will have 97% power to detect a treatment difference of -0.6% in mean HbA1c change from Baseline to Week 26 between sotagliflozin 400 mg and placebo.

This sample size will also allow to exclude a decline in BMD from Baseline of >2% with a 95% power, assuming a missing rate of 30% and an SD of 3.5%.

The total sample size will be approximately 360 patients to be randomized (120 in sotagliflozin 200 mg group, 120 in sotagliflozin 400 group, and 120 in placebo group).

Calculations were made using East 6.4 software.

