For patients in the sotagliflozin groups with missing data at Week 26 (or Week 12 for SBP), their missing values will be imputed using observed baseline and the observed primary endpoint data from placebo completers; no intermittent values from either placebo or the active treatment groups will be used.

For placebo patients, missing data will be imputed based on the placebo group data. Intermittent observed values will be used while imputing missing values at Week 26 (or Week 12 for SBP). In cases that a non-monotone missing data pattern occurs at the intermediate visits, these data points will be first imputed in the placebo group using the Markov Chain Monte Carlo (MCMC) option in PROC MI to achieve a monotone missing pattern for all placebo patients. The Week 26 (or Week 12 for SBP) endpoint values will be subsequently imputed from the multiple copies of the original dataset where each copy will have a monotone missing pattern.

The imputation models for the washout MI method will include the randomization strata and the corresponding baseline value. Missing data will be imputed using the regression method. In cases of non-convergence during the imputations, especially for the MCMC application in the placebo non-monotone datasets, graphical measures (eg, trace and autocorrelation plots) will be used to identify the offending variable and once detected, that variable(s) will be dropped from the model and the imputations will be re-run. These re-run models will use the same seed number and number of imputations as used in the original models.

Using either imputation method, missing endpoint data will be imputed 2000 times to generate multiple data sets with complete data. Other details of the imputation procedures such as the seed number and sort ordering are specified in the SAS programs. The HbA1c change from Baseline to Week 26 will be derived from observed and imputed HbA1c values at Week 26.

Each of the completed datasets after the imputation will be analyzed using the Analysis of Covariance (ANCOVA) model with treatment groups (sotagliflozin 400 mg, sotagliflozin 200 mg, placebo), randomization stratum of HbA1c ($\leq 8.5\%$, $> 8.5\%$), randomization stratum of sex (male, female), and country as fixed factors, and baseline value of the efficacy endpoint as a covariate.

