Categorical endpoint of HbA1c $<$ 7% at week 26 will be analyzed using a Cochran-Mantel-Haenszel (CMH) method stratified by randomization stratum of HbA1c (\leq 8.5%, $>$ 8.5%), and randomization stratum of sex (male, female). Proportion of HbA1c responders in each treatment group will be provided with the difference between each sotagliflozin group and placebo group and their associated 2-sided 95% CI. To determine whether a patient is HbA1c responder or not, all measurements at week 26 will be used regardless of discontinuation of IMP or initiation of rescue medication. Patients with no HbA1c measurement at week 26 will be treated as non-responders. Summary tables and graphs will be provided by treatment group at scheduled visit.

For between-group comparison for HbA1c $<$ 7% responder analysis, a sensitivity analysis will be performed by excluding patients with baseline HbA1c $<$ 7% using the same CMH test mentioned above. Similarly, by-visit summary based on above subset of patients may be provided.

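### The HbA1c <7.0% responder analysis is valid but leaves out measured baseline HbA1c, at a cost of roughly 1.5 to 3 points of power on a nominal test

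*Protocol*

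**What the plan says.** Protocol 11.4.2.2 states that the Week 26 responder endpoint "will be analyzed using a Cochran-Mantel-Haenszel method stratified by randomization stratum of Screening HbA1c" (≤8.5%, >8.5%) and by sex. SAP 2.4.4.2 agrees: it "will be analyzed using a Cochran-Mantel-Haenszel (CMH) method stratified by randomization stratum of HbA1c" and sex. Both promise a difference in proportions with a 95% CI for each dose against placebo, and neither says how that interval is computed. On missing data the protocol says: "Patients who have no HbA1c measurement at Week 26 will be treated as nonresponders".

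The SAP adds a sensitivity analysis that repeats the CMH without patients whose baseline HbA1c is below 7%.

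The continuous HbA1c analysis is built differently. Protocol 11.4.2.1 fits treatment, both strata and country "and Baseline HbA1c value as a covariate". SAP 2.4.4.1 likewise uses the "baseline value of the efficacy endpoint as a covariate". The measurement is available: Protocol 9.1.4.1 schedules HbA1c at Visit 3.

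Superiority on the responder endpoint is a secondary objective for both doses (Protocol 5.2, SAP 1.2.2), but the endpoint is in neither document's fixed sequence (Protocol 11.4.2.4, SAP 2.4.4.4).

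**The concern.** Screening HbA1c may run from 7.0% to 11.0% (Protocol 7.2.2, E 14), so the lower stratum spans 7.0% to 8.5%. Within it, the distance a patient must fall to get below 7.0% varies widely, and the CMH treats all these patients of one sex as exchangeable. The variable that separates them is measured and is already modelled for the continuous endpoint. At stake is some precision in the difference in responder proportions and some power for its nominal test, with the same patients and visits.

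**Working it through.** **The plan's own figure.** Protocol 11.1: "Assuming a common standard deviation (SD) of 1.2% and using a 2-sided test at a 0.05" level, 120 per arm "will have 97% power to detect a treatment difference of -0.6% in mean HbA1c change from Baseline to Week 26". SE = 1.2 × √(2/120) = 0.1549; 0.6/0.1549 = 3.873; Φ(3.873 − 1.960) = Φ(1.913) = 97.2% (97.1% with the noncentral t). The stated 97% reproduces. Neither document gives a responder rate or responder power, so the rest is simulation.

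**Inputs from the documents.** 120 per arm; two-sided 0.05; difference −0.6% and SD 1.2% (Protocol 11.1); screening range 7.0–11.0%; placebo change about −0.1% (−0.09% in the Phase 2 study, Protocol 4.3); missing counted as nonresponse.

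**Assumptions not in the documents.** Screening HbA1c normal, truncated to 7–11% (central case: underlying mean 8.2, SD 0.9); screening-to-baseline noise SD 0.2 to 0.4; slope of change on baseline 0 to −0.5; residual SD 0.9 to 1.2; missing 0 to 30%.

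**Model.** Week 26 = baseline − 0.1 + slope × (baseline − 8.2) − 0.6 × treated + error.

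**Why baseline matters within a stratum.** Take the central case (slope −0.3, residual SD 1.16), placebo, before missing data:
- Baseline 7.1: expected 7.1 − 0.1 + 0.33 = 7.33; P(<7.0) = Φ(−0.33/1.16) = 39%.
- Baseline 8.4: expected 8.4 − 0.1 − 0.06 = 8.24; P(<7.0) = Φ(−1.24/1.16) = 14%.

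**Tests compared on the same simulated data.**
- CMH over four strata (stratum × sex), no continuity correction: [Σ(a − n₁m/N)]² / Σ[n₁n₀m(N − m)/(N²(N − 1))], against 3.84. Here a is treated responders, m all responders, and n₁ and n₀ the arm sizes in a stratum of size N.
- Logistic regression with treatment, stratum, sex and baseline HbA1c; likelihood-ratio test.
- Standardized risk difference from that model: the mean over all patients of p̂(treated) − p̂(placebo), divided by an influence-function standard error.

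5,000 trials per row, 10% missing:

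| Difference | Slope | Residual SD | CMH | Logistic + baseline | Standardized difference |
|---|---|---|---|---|---|
| −0.6 | −0.3 | 1.16 | 71.0% | 72.5% | 72.1% |
| −0.6 | −0.5 | 1.1 | 77.5% | 78.9% | 78.3% |
| −0.6 | 0 | 1.2 | 65.1% | 68.5% | 68.0% |
| −0.6 | 0 | 0.9 | 78.3% | 83.1% | 82.6% |
| −0.45 | 0 | 1.0 | 49.4% | 54.9% | 54.2% |
| 0 | −0.3 | 1.16 | 4.4% | 5.1% | 4.8% |

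The Monte Carlo SE of a power figure is about 0.7 points. A 4,000-trial run of the first row gave 71.3% against 73.6% (CMH, then logistic). Other 4,000-trial cases at slope −0.3, again CMH then logistic: 30% missing, 57.0% and 59.3%; difference −0.34 (the Phase 2 value for 200 mg, Protocol 4.2), 28.0% and 30.1%; screening noise 0.4, 69.1% and 72.3%.

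Two further simulations used their own settings:
- One (6,000 trials, 8% missing) gave 75.5% and 78.0%, and 72.2% and 75.1%, at SD about 1.2 and difference −0.6. The variance of the risk difference fell by about 3–8%.
- The other compared the CMH with the standardized difference: 69.9% and 72.8% in its central case, 63.0% and 67.9% at slope 0, and 76.7% and 78.4% at slope −0.5. Type I error was 5.1% and 5.3%.

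**Interval width.** At rates of 15.5% and 29%, the unadjusted half-width is 1.96 × √[(0.155 × 0.845 + 0.29 × 0.71)/120] = 10.4 points. A 3–8% variance reduction multiplies it by √0.97 to √0.92, which is 0.2 to 0.4 points narrower.

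**The case against.** The planned analysis is sound. A CMH on the randomization strata follows the allocation scheme, already uses screening HbA1c at one cut, suits a difference in proportions, needs no outcome model, and is the same in both documents. No stated responder power is missed, because none is stated. All of this stands: a reader might infer that the test is wrong or inconsistent with the rest of the plan, and it is neither.

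Part of the gain is not due to baseline. The CMH ran slightly below nominal size (4.4%). Against a logistic model without baseline, the covariate itself adds about 0.5 to 4.7 points. This stands too, and it leaves a gain.

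A reader might also take the responder test to be the only efficacy analysis without baseline adjustment. The contrast holds only for the tested endpoints: the primary and the continuous secondary endpoints adjust for their own baseline value, while the other continuous efficacy endpoints are descriptive (Protocol 11.4.2.3, SAP 2.4.4.3).

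Nor would the covariate make the SAP's sensitivity analysis redundant. Excluding patients already below 7% at baseline asks whether patients newly reach the target. Adjusting for baseline does not answer that.

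**Conclusion.** This is an efficiency point of low importance. Adding baseline HbA1c raised power in every scenario run: by 1.4 to 5.5 points for the logistic test and 0.9 to 4.8 for the standardized difference in the main runs, with type I error near 5%. At plan-like inputs (−0.6%, SD about 1.2%, change depending on baseline) the gain is roughly 1.5 to 3 points.

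A reader might quote the upper end as a property of this trial. The documents do not support that: gains near 5 points arise mainly when change is unrelated to baseline, or at a smaller SD or effect than the plan's, and the distribution, slope and missing rate are all assumed.

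Because superiority here is a stated objective, a reader might also infer that a confirmatory claim is at risk. It is not. Both documents disclaim multiplicity adjustment for endpoints outside the sequence, so the gain affects only a nominal p-value and slightly narrows its interval.

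**What to change.** Amend SAP 2.4.4.2 and Appendix C before the first-step unblinding:

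- Make the main responder analysis a logistic regression with treatment, the two randomization strata and continuous baseline HbA1c, with missing Week 26 values still counted as nonresponse.
- Take both the p-value and the 95% CI from the standardized (marginal) risk difference, and name its variance method (delta method or bootstrap). Test and interval then agree, the planned effect measure is kept, and the unspecified interval method is settled.
- Keep the stratified CMH as the supportive analysis.
- Keep the sensitivity analysis that excludes patients with baseline HbA1c below 7%.

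The cost is SAP wording and one model, with no new data, visits or patients. The downside is reliance on a model-based test, which the retained CMH offsets.

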#### **11.4.2.3 Analysis of other efficacy endpoints**

The analysis of other efficacy endpoints will be descriptive with no formal testing. Summary statistics at scheduled visits using OC will be provided by each treatment group. Graphical presentations will also be used to illustrate trends over time

#### **11.4.2.4 Multiplicity considerations**

To control the family-wise Type I error, a fixed sequence testing approach will be used to test primary and secondary endpoints. Only if the difference in mean change from Baseline to Week 26 in HbA1c of sotagliflozin 400 mg versus placebo is statistically significant at  $\alpha = 0.05$  (2-sided), a hierarchical testing procedure will be performed to test the secondary endpoints in the following prioritized order:

- Superiority of sotagliflozin 400 mg versus placebo with respect to:
  - Change from Baseline to Week 26 in BW.

- Change from Baseline to Week 26 in FPG.
- Change from Baseline to Week 12 in SBP for all patients.
- Superiority of sotagliflozin 200 mg versus placebo with respect to:
  - Change from Baseline to Week 26 in HbA1c.
  - Change from Baseline to Week 26 in BW.
  - Change from Baseline to Week 26 in FPG.
  - Change from Baseline to Week 12 in SBP for all patients.

Superiority tests will be tested at 2-sided 5% significant level. If any of the endpoints is found to be not statistically significant, the testing procedure will be stopped and the following endpoints will not be tested. Multiplicity adjustment will not be performed on other secondary endpoints not mentioned above.

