### 5.2 SECONDARY

The secondary objectives of this study are:

- To compare the effects of sotagliflozin 400 mg and 200 mg versus placebo with respect to the percent change from Baseline to Week 26 in BMD (lumbar spine, total hip, and femoral neck) measured by DXA (key secondary safety objective).
- To demonstrate the superiority of sotagliflozin 400 mg versus placebo on:
  - Change from Baseline to Week 26 in BW.
  - Change from Baseline to Week 26 in FPG.
  - Change from Baseline to Week 12 in SBP for all patients.
  - Proportion of patients with HbA1c <7.0% at Week 26.
- To demonstrate the superiority of sotagliflozin 200 mg versus placebo with respect to:
  - HbA1c reduction from Baseline to Week 26.
  - Change from Baseline to Week 26 in BW.
  - Change from Baseline to Week 26 in FPG.
  - Change from Baseline to Week 12 in SBP for all patients.
  - Proportion of patients with HbA1c <7.0% at Week 26.
- To evaluate the safety of sotagliflozin 200 mg and 400 mg compared with placebo over the 104 weeks of treatment.

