##### 9.1.2.2 Secondary efficacy endpoints

- Change from Baseline to Week 26 in HbA1c (sotagliflozin 200 mg only).
- Change from Baseline to Week 26 in BW.
- Change from Baseline to Week 26 in FPG.
- Change from Baseline to Week 12 in SBP for all patients.
- Proportion of patients with HbA1c <7.0% at Week 26.

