1.2.2 Secondary objectives

The secondary objectives of this study are:

- To compare the effects of sotagliflozin 400 mg and 200 mg versus placebo with respect to the percent change from Baseline to Week 26 in Bone Mineral Density (BMD) (lumbar spine, total hip, and femoral neck) measured by dual-energy X-ray absorptiometry (DXA) (key secondary safety objective).
- To demonstrate the superiority of sotagliflozin 400 mg versus placebo on:
 - Change from Baseline to Week 26 in body weight (BW),
 - Change from Baseline to Week 26 in fasting plasma glucose (FPG),
 - Change from Baseline to Week 12 in systolic blood pressure (SBP) for all patients,
 - Proportion of patients with HbA1c <7.0% at Week 26.
- To demonstrate the superiority of sotagliflozin 200 mg versus placebo with respect to:
 - HbA1c reduction from Baseline to Week 26,
 - Change from Baseline to Week 26 in BW,
 - Change from Baseline to Week 26 in FPG,
 - Change from Baseline to Week 12 in SBP for all patients,
 - Proportion of patients with HbA1c <7.0% at Week 26.
- To evaluate the safety of sotagliflozin 200 mg and 400 mg compared with placebo over the 104 weeks of treatment.

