2.4.4 Analyses of efficacy endpoints

Efficacy analyses will be performed on the ITT population using the efficacy assessments collected during the study, including those obtained after IMP discontinuation or introduction of rescue therapy (de facto estimand), unless otherwise specified.

Statistical testing will be performed for primary endpoint and secondary endpoints at Week 26 (or Week 12 for SBP). The superiority tests will be two-sided tests at nominal 5% significance level. All efficacy endpoints, other than primary and main secondary efficacy endpoints, will only be summarized by descriptive statistics without formal statistical testing.

Missing data for efficacy analyses is identified through steps described in [Section 2.5.4](#).

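### HbA1c <7.0% at Week 26 is a superiority objective for both doses but sits outside the fixed sequence; adding it as the last two steps would be a free improvement

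*Protocol*

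**What the plan says.** Protocol 5.2 heads one list of secondary objectives "To demonstrate the superiority of sotagliflozin 400 mg versus placebo on" and includes in it "Proportion of patients with HbA1c <7.0% at Week 26". The list for the lower dose holds the same item. SAP 1.2.2 repeats both lists, the second headed "To demonstrate the superiority of sotagliflozin 200 mg versus placebo with respect to". Protocol 9.1.2.2 names five secondary efficacy endpoints: HbA1c change (200 mg only), body weight, fasting plasma glucose, Week 12 systolic blood pressure, and the responder proportion.

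Testing is planned for all of them. Protocol 11.4.2 says "Statistical testing will be performed for primary endpoint and secondary endpoints at Week 26 (or Week 12 for SBP"), and SAP 2.4.4 adds "The superiority tests will be two-sided tests at nominal 5% significance level". The responder comparison of each dose with placebo uses a Cochran-Mantel-Haenszel (CMH) test stratified by screening HbA1c and sex (Protocol 11.4.2.2, SAP 2.4.4.2).

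The fixed sequence in Protocol 11.4.2.4, the synopsis and SAP 2.4.4.4 has eight tests, and the responder endpoint is in none of these lists. For whatever is not listed, the protocol states "Multiplicity adjustment will not be performed on other secondary endpoints not mentioned above", and SAP 2.4.4.4 says the same in other words. The change table in SAP 1.6 records that version 2, approved 11-Oct-2018, took the endpoint out of the SAP hierarchy for both doses to match the protocol.

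**The concern.** An objective worded as a demonstration of superiority normally has a test whose error rate the plan controls. Here two such objectives, one per dose, have only a nominal test. If all eight listed tests succeed, the plan still has no route to a controlled claim on reaching HbA1c below 7.0%. The Week 26 results are final at the first-step analysis and go into the submission dossier (Protocol 11.5). A responder p-value below 0.05 could be read there as meeting a stated objective, although the multiplicity section supports no more than a nominal statement.

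**Working it through.** **1. Objectives against the sequence.**

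| Endpoint | 400 mg | 200 mg |
|---|---|---|
| HbA1c change, Week 26 | step 1 (primary) | step 5 |
| Body weight, Week 26 | step 2 | step 6 |
| Fasting plasma glucose, Week 26 | step 3 | step 7 |
| Systolic blood pressure, Week 12 | step 4 | step 8 |
| HbA1c <7.0%, Week 26 | objective, no step | objective, no step |

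Bone mineral density is also outside the sequence, but it is a safety endpoint for which no significance test is planned (Protocol 11.4.3.1). The responder proportion is therefore the only secondary efficacy endpoint left out.

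**2. The plan's own power figure.** Inputs from Protocol 11.1: SD 1.2%, 120 per arm, difference 0.6%, two-sided 0.05.
- SE = 1.2 × √(2/120) = 0.155.
- 0.6/0.155 = 3.87, and power = Φ(3.87 − 1.96) = 97.2% (97.1% with the t distribution). The stated 97% is reproduced.

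**3. Control as written.** In a fixed sequence, a false rejection requires rejecting the first true null in the order, and that test has level 0.05. Family-wise error over the eight tests is therefore at most 0.05 two-sided, or 2.5% in favour of sotagliflozin. What happens outside the sequence does not alter this.

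**4. Effect of two more steps at the end.** The level of each of steps 1 to 8, and the condition for reaching it, stay the same, so their error and power do not change. The argument in item 3 then covers ten tests, still at 0.05.

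**5. How often the new steps would be reached.** All eight tests must succeed, so the chance cannot exceed the power of any one of them. For step 5, using the same SE and the 12-week phase 2 results:
- LS mean difference 0.34% (Protocol 4.2): 0.34/0.155 = 2.19; power about 59%.
- Raw difference 0.52 − 0.09 = 0.43% (Protocol 4.3): 0.43/0.155 = 2.78; power about 79%.

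The documents give no responder rates, so the power of the new steps themselves cannot be stated.

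**6. What would follow if the nominal responder p-values were read as claims regardless of the sequence.** The responder status comes from the same Week 26 HbA1c measurements as the mean change (Protocol 11.4.2.2: "all values at Week 26 will be used to determine whether a patient is a responder or not"), so the two statistics are correlated. Cutting a normal variable at responder proportion p gives a correlation of φ(c)/√(p(1−p)), where c is the p-quantile. This is 0.58 at an assumed p = 10% and 0.80 at p = 50%, which is its maximum. The calculation ignores covariate adjustment and the rule that missing counts as nonresponse. The simulation used three independent arms with a shared placebo (between-dose correlation 0.5), a critical value of 1.96 and 4,000,000 draws. False claims in favour of sotagliflozin, with two-sided rates in brackets:
- No effect at either dose; primary or either responder test: 5.8% to 6.3% (11.6% to 12.6%).
- 400 mg effective, 200 mg null, sequence reaching step 5; 200 mg HbA1c or 200 mg responder: 3.9% to 4.4% (7.8% to 8.8%).
- The sequence alone: 2.5% (5%).

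**The case against.** The strongest reply is that this is a design choice, openly made. Which secondary endpoints belong to the confirmatory family is for the sponsor to decide. Both documents say the rest are unadjusted, SAP 2.4.4 calls the level nominal, and SAP 1.6 shows the protocol and SAP being brought into line. All of that stands. The estimates, confidence intervals and CMH tests would be the same with or without the extra steps; only the standing of two p-values differs.

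A reader might infer from item 6 of the working that the trial's family-wise error exceeds 5%. The documents do not support that, because they make no controlled claim on the responder endpoint. The first case also needs the responder tests to count when the primary has failed. Protocol 11.4.2.4 makes testing of the secondary endpoints conditional on the primary, in a sentence that introduces a list without the responder endpoint, while Protocol 11.4.2 plans testing in general terms. The gating is thus unclear. If the responder tests are read as following the primary, the rate with no effect at either dose is at most 2.5% (5% two-sided).

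It can also be said that the remedy brings little, since eight successes are needed first. That is right and limits the weight of the point. It does not remove the case for a change that takes nothing from the existing tests.

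**Conclusion.** The point holds as a free improvement and not as an error. Two objectives worded as superiority have no error-controlled test, even in the best case where every listed comparison succeeds. No conclusion on the primary or the seven listed secondary tests is affected. A reader might also infer that the protocol and SAP conflict, or that the endpoint was dropped without notice. Neither is so: the multiplicity sections agree and the change is recorded.

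The size is minor. The benefit is a possible controlled claim on two objectives, with the chance of reaching the new steps capped at about 59% to 79%. That cap assumes SD 1.2%, 120 evaluable patients per arm and 12-week phase 2 effects that persist to Week 26. The other seven steps can only lower it. The rates in item 6 describe a misreading of nominal p-values and are not the trial's error rate.

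**What to change.** Before Week 26 unblinding only, append two steps after the 200 mg systolic blood pressure test: HbA1c <7.0% for 400 mg, then for 200 mg. Make the change in Protocol 11.4.2.4, the synopsis and SAP 2.4.4.4. Use the planned CMH test at two-sided 5% for each, and state that the results are confirmatory only if all eight earlier tests succeed and are nominal otherwise.

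The cost is a protocol amendment (Protocol 15) and an SAP update. No new data or analysis is needed, and no alpha or power is taken from the existing tests. The first patient was enrolled on 14-Mar-2018 (SAP 1.5) and SAP version 3 is dated 30 January 2020. The documents do not say whether first-step unblinding had taken place by then. If it has, the sequence should stay as it is, and the responder results remain unadjusted, as both documents already state.
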